**Only enough drug for one 28 day cycle will be supplied at a time.**

#### 8.2.11 **Pregnancy Risk**

Thalidomide is a powerful human teratogen, inducing a high frequency (about 30%) of severe and live-threatening birth defects such as: ectromelia (amelia, phocomelia, hemimelia) of the upper and/or lower extremities, microtia with abnormality of the external acoustic meatus (blind or absent), middle and internal ear lesions (less frequent), ocular lesions (anophthalmia, microphthalmia), congenital heart disease, renal abnormalities. Other less frequent abnormalities have also been described.

Females of childbearing potential (FCBP) must agree to use two reliable forms of contraception simultaneously or to practice complete abstinence from heterosexual contact during the following time periods related to this study: 1) for at least 4 weeks before starting study drug; 2) while taking study drug; 3) during dose interruptions and 4) for at least 4 weeks after discontinuation of the study drug. The two methods of reliable contraception must include one highly effective method (i.e. intrauterine device (IUD), hormonal [birth control pills, injections, patch or vaginal implants], tubal ligation, partner's vasectomy) and one additional effective (barrier) method (i.e. male condom, diaphragm, cervical cap). The FCBP must be referred to a qualified provider of contraceptive methods if needed.

Combined hormonal contraceptives are not recommended due to the increased risk of venous thrombo-embolic disease. The choice of contraceptive methods should necessitate a risk/benefit discussion between the patient and a qualified physician experienced in the use of contraceptive methods. Effective measures to avoid pregnancy must be taken.

Implants and levonorgestrel-releasing intrauterine systems are associated with an increased risk of infection at the time of insertion and irregular vaginal bleeding. Prophylactic antibiotics should be considered particularly in patients with neutropenia.

Copper-releasing intrauterine devices are generally not recommended due to the potential risks of infection at the time of insertion and menstrual blood loss which may compromise patients with neutropenia or thrombocytopenia

#### Criteria for females of childbearing potential (FCBP)

Two categories:

1 – Females not of childbearing potential include females who have had a natural menopause for at least 24 consecutive months, a hysterectomy, and/or bilateral oophorectomy

2 – Females of childbearing potential are all other females who are menstruating, amenorrheic from previous medical treatments, under 50 years of age, and/or perimenopausal

#### 8.2.12 **Pregnancy Testing**

Pregnancy tests must occur within 10 – 14 days and again within 24 hours prior to prescribing Thalidomide for Cycle 1 (prescriptions must be filled within 7 days). FCBP with regular or no menstruation must have a pregnancy test weekly for the first 28 days and then every 28 days while on therapy (including breaks in therapy); at discontinuation of thalidomide and at Day 28 post the last dose of thalidomide. Females with irregular menstruation must have a pregnancy test weekly for the first 28 days and then every 14 days while on therapy (including breaks in therapy), at discontinuation of thalidomide and at Day 14 and Day 28 post the last dose of thalidomide (see Appendix A: Risks of Fetal Exposure, Pregnancy Testing Guidelines and Acceptable Birth Control Methods).

### 8.3 **Rituximab**

#### 8.3.1 **Chemistry**

Rituximab is a genetically engineered chimeric murine/human monoclonal antibody directed against the CD20 antigen found on the surface of normal and malignant B-lymphocytes. The antibody is an IgG1 kappa immunoglobulin containing murine light- and heavy-chain variable region sequences and human constant region sequences. The Fab domain of rituximab binds to the CD20 antigen on B lymphocytes, and the Fc domain recruits immune effector functions to mediate B-lymphocyte lysis in vitro. Possible mechanisms of cell lysis include complement-dependent cytotoxicity (CDC) and antibody dependent cell mediated cytotoxicity (ADCC). The antibody has been shown to induce apoptosis in the DHL-4 human B-cell lymphoma line.

#### 8.3.2 **Pharmacology and Pharmacokinetics**

In prior studies patients treated at the 375 mg/m^2 dose levels exhibited detectable antibody concentrations throughout the treatment period. Most patients exhibited increasing pre-infusion antibody concentrations with each subsequent infusion. In nine patients, the T1/2 following the first antibody infusion was 59.8 hours (11.1-104.6 hr) with a Cmax of 271 µg/ml. Following the fourth antibody infusion when circulating B cells had been depleted and antigenic sites coated, the T1/2 was 174 hr (26.4-442.3 hr) and Cmax 496.7 µg/ml.

#### 8.3.3 **Human Toxicology**

No dose-limiting effects were observed in the Phase I/II studies. Reported adverse events including fever, chills, headache, nausea, vomiting, rhinitis, asthenia, and hypotension, occurred primarily during rituximab infusions and typically responded to an interruption of the infusion and resumption at a slower rate.

**Fatal Infusion Reactions:** Severe and fatal cardiopulmonary events, including angioedema, hypoxia, pulmonary infiltrates, acute respiratory distress syndrome, myocardial infarction, and cardiogenic shock, have been reported. These severe reactions typically occurred during the first infusion with time to onset of 30-120 minutes.

**Cardiac Events:** Patients with preexisting cardiac conditions, including arrhythmia and angina, have had recurrences of these cardiac events during rituximab infusions.

**Tumor Lysis Syndrome:** Tumor lysis syndrome has been reported and is characterized in patients with a high number of circulating malignant cells ( $\geq 25,000/\text{mm}^3$ ) by rapid reduction in tumor volume, renal insufficiency, hyperkalemia, hypocalcemia, hyperuricemia, and hyperphosphatemia.

**Renal Events:** Rituximab has been associated with severe renal toxicity including acute renal failure requiring dialysis, and in some cases has led to death. Renal toxicity has occurred in patients with high numbers of circulating malignant cells ( $\geq 25,000/\text{mm}^3$ ) or high tumor burden who experience tumor lysis syndrome and in patients administered concomitant cisplatin.

**Mucocutaneous Reactions:** Severe bullous skin reactions, including fatal cases of toxic epidermal necrolysis and paraneoplastic pemphigus, have been reported in patients treated with rituximab. The onset of reaction has varied from 1 to 13 weeks following rituximab exposure.

**Hematologic Events:** In clinical trials, Grade 3 and 4 cytopenias were reported in 48% of patients treated with rituximab; these include: lymphopenia (40%), neutropenia (6%), leukopenia (4%), anemia (3%), and thrombocytopenia (2%). The median duration of lymphopenia was 14 days (range, 1 to 588 days) and of neutropenia was 13 days (range, 2 to 116 days). A single occurrence of transient aplastic anemia (pure red cell aplasia) and two occurrences of hemolytic anemia following Rituximab therapy were reported.

In addition, there have been a limited number of postmarketing reports of prolonged pancytopenia, marrow hypoplasia, and late onset neutropenia.

**Infectious Events:** Rituximab induced B-cell depletion in 70% to 80% of patients with NHL and was associated with decreased serum immunoglobulins in a minority of patients; the lymphopenia lasted a median of 14 days (range, 1-588 days). Infectious events occurred in 31% of patients: 19% of patients had bacterial infections, 10% had viral infections, 1% had fungal infections, and 6% were unknown infections. Serious infectious events (Grade 3 or 4), including sepsis, occurred in 2% of patients.

**Hepatitis B Reactivation:** Hepatitis B virus (HBV) reactivation with fulminant hepatitis, hepatic failure, and death has been reported in some patients with hematologic malignancies treated with rituximab. The majority of patients received rituximab in combination with chemotherapy. The median time to the diagnosis of hepatitis was approximately four months after the initiation of rituximab and approximately one month after the last dose.

**Other Serious Viral Infections:** The following additional serious viral infections, either new, reactivated or exacerbated, have been identified in clinical studies or postmarketing reports. The majority of patients received Rituxan in combination with chemotherapy or as part of a hematopoietic stem cell transplant. These viral infections included JC virus (progressive multifocal leukoencephalopathy [PML]), cytomegalovirus, herpes simplex virus, parvovirus B19, varicella zoster virus, West Nile virus, and hepatitis C. In some cases, the viral infections occurred up to one year following discontinuation of Rituxan and have resulted in death.

**Progressive multifocal leukoencephalopathy (PML):** PML is a rare and demyelinating disease of the brain caused by infection with the JC virus that usually leads to death or severe disability. JC virus infection resulting in PML and death has been reported rarely in patients with hematologic malignancies receiving rituximab. The majority of these patients had received rituximab in combination with chemotherapy or as part of a hematopoietic stem cell transplant. Cases of PML resulting in death have also been reported in patients with systemic lupus erythematosus (SLE) treated with rituximab. These patients with SLE had longstanding disease, history of prior immunosuppressant therapy, and were diagnosed with PML within 12 months of their last infusion of rituximab.

Physicians should consider PML in any patient presenting with new onset neurologic manifestations. Consultation with a neurologist, brain MRI, and lumbar puncture should be considered as clinically indicated. In patients who develop PML, rituximab should be discontinued and reductions or discontinuation of any concomitant chemotherapy or immunosuppressive therapy should be considered.

**Bowel Obstruction and Perforation:** Abdominal pain, bowel obstruction and perforation, in some cases leading to death, were observed in patients receiving Rituxan in combination with chemotherapy for DLBCL. In post-marketing reports, which include both patients with low-grade or follicular NHL and DLBCL, the mean time to onset of symptoms was 6 days (range 1–77) in patients with documented gastro-intestinal perforation. Complaints of abdominal pain, especially early in the course of treatment, should prompt a thorough diagnostic evaluation and appropriate treatment.

**Additional Safety Signals:** The following serious adverse events have been reported to occur in patients following completion of rituximab infusions: arthritis, disorders of blood vessels (vasculitis, serum sickness and lupus-like syndrome), eye disorders (uveitis and optic neuritis), lung disorders including pleuritis and scarring of the lung (bronchiolitis obliterans), that may result in fatal outcomes, and fatal cardiac failure.

#### 8.3.4 **Formulation**

Rituximab is commercially available in 10 mL and 50 mL single-use vials containing 100 mg or 500 mg rituximab solution, respectively, at a concentration of 10 mg/mL.

#### 8.3.5 **Storage and Stability**

Intact vials should be stored under refrigeration (2°-8°C). Dilute solutions for infusion (1-4 mg/mL) are stable for 24 hours under refrigeration, and for an additional 24 hours at room temperature. The desired dose of rituximab should be diluted in 0.9% NaCl or D5W to a final concentration of 1-4 mg/mL. The solution should be mixed by gently inverting the bag.

#### 8.3.6 **How Supplied**

Rituximab will be obtained from commercial stock from the non-investigational pharmacy and, along with its administration costs, will be billable to the patient.

#### 8.3.7 **Rituximab Administration**

Rituximab will be administered on days 1, 8, 15 and 22 starting with Cycle 1 and then again on the same weekly x 4 schedule every 6th cycle through Cycle 19 (Cycles 7, 13, and 19). All patients should be premedicated with acetaminophen 650 mg and diphenhydramine 25-50 mg (or equivalent) 30 minutes prior to the rituximab. Rituximab 375 mg/m^2 will be administered by IV infusion starting at a rate of 50 mg/hour. If no infusion related reactions occur, the infusion rate should be escalated in 50 mg/hour increments every 30 minutes to a maximum of 400 mg/hour until the infusion is completed. Vital signs will be monitored every 15 minutes while infusion rate is being escalated.

## 9. CORRELATIVE/SPECIAL STUDIES

See Section 5.1 for specific dosing instructions

**Cycle -1:** Half of the patients will receive 14 days of thalidomide 50 mg PO daily, followed by 14 days off and the other half of the patients will receive 14 days of lenalidomide 5 mg PO daily, followed by 14 days off

**Cycle 1 and beyond:** Alternating thalidomide and lenalidomide continuously

Samples will be collected for correlative studies to be performed in association with the trial. The following samples will be collected:

### 1. CLL Prognostic Profiles\*:

Samples will be analyzed as described in the Schedule of Assessments (Section 10) and will include:

- 1) IgVH Mutation Analysis
- 2) Zap-70 expression by immunohistochemistry
- 3) CD38, CD 5, CD19/CD20, CD 23, sIg
- 4) Interphase FISH for trisomy 12, deletion 17p, deletion 13q14, deletion 11q23 (blood and bone marrow)
- 5) Purified CLL cell interphase FISH (not called Purified on calendar)
- 6) beta-2-microglobulin

### 2. BLyS/BAFF Analysis\*

- 1) Measurement of serum levels of BLyS and APRIL
  - a. day 1 and 15 of cycle -1 (prior to administration of study agents).
  - b. immediately prior to rituximab at cycles 1, 7, 13, and 19, and then prior to the last dose of rituximab (day 22) for that cycle.
- 2) BLyS expression on monocytes:
  - a. day 1 and 15 of cycles -1 (prior to administration of study drug)
  - b. day 1 and 15 of cycle 1 (immediately prior to Rituximab administration)
- 3) BLyS receptor expression on CLL cells:
  - a. Prior to administration of study drug on days 1 and 15 of cycles -1
  - b. Immediately prior to administration of Rituximab on days 1 and 15 of Cycle 1
- 4) BLyS gene polymorphisms: baseline
- 5) MMP-9 activity: baseline

### 3. Impact of IMiD therapy on TNF Family and cox Family mRNA stability\*:

- 1) Impact on p38 MAPK activity: day 1, 15 of cycles -1 and 1 prior to administration of study drugs

- 2) TNF-alpha / cox-2 / BAFF mRNA levels: day 1, 15 of cycles -1 and 1 prior to administration of study drugs
  - 3) Level of HuR binding to TNF-alpha / cox-2 mRNA / BAFF mRNA: day 1, 15 of cycles -1 and 1 prior to administration of study drugs
4. RNA Expression Arrays\*
- Changes in RNA expression resulting from the IMiD therapy will be assessed using RNA expression arrays. Samples to be assessed:
- 1) CLL cells: day 1, 2, and 15 of cycles -1 and 1 prior to administration of study drug
  - 2) T cells: day 1, 2, and 15 of cycles -1 and 1 prior to administration of study drug
  - 3) Monocytes: day 1, 2, and 15 of cycles -1 and 1 prior to administration of study drug
5. Methylation Arrays\*
- Changes in gene methylation patterns resulting from IMiD therapy will be assessed using methylation oligomicroarrays (MOMA) at:
- Day 1 and 15 of cycles -1 and 1 prior to administration of study drug
6. Metabolomics\*: day 1, 15 of cycles -1 and 1 prior to administration of study drug
7. Peripheral Blood Activation Markers\*
- Changes in cell surface markers will be assessed by flow cytometry and will include: CD38, HLA-DR, CD25: Prior to administration of study drug in Cycle -1, 1 and 2 on Days 1 and 15.
8. Peripheral Blood Cell Subset Analysis\*
- Changes in peripheral blood mononuclear cell subsets: baseline; Cycle 1 prior to administration of study drug on days 1 and 15 ; Cycles 2 and 3 prior to administration of study drug on Day 1; every three cycles for Cycle 6 through Cycle 24; followed by every six cycles thereafter.
- Panel to include:
- CD3/CD4/CD8: T cell subsets
  - CD16/CD56: NK cells
  - CD14: monocytes
  - CD3/CD25/FoxP3: regulatory T cells
  - Circulating Endothelial cell precursors
9. VEGF Analysis\* prior to administration of study drug in Cycles -1, 1 and 2 on Days 1 and 8.
- 1) VEGF, bFGF serum levels
  - 2) Changes in VEGF Receptor expression profile

10. Genetic polymorphisms predictive of response\* prior to administration of study drug in Cycles -1, 1 and 2 on Days 1 and 15.

- 1) TNF-alpha
- 2) BAFF

11. T-cell Repertoire Studies: samples will be collected prior to treatment on cycle -1 and prior to cycles 6, 12, and 24 and evaluated for T-cell Repertoire

12. PI 3-Kinase Assessment: samples will be assessed for PI 3-Kinase activity levels prior to cycle -1, day 15 of cycle -1, and day 15 of cycle #1.

\*\*\*\* Rituximab can be given +/- 2days.

\*\*\*\*All correlative work must be drawn prior to Rituximab administration regardless of the day Rituximab is given.

\* See Section 10 for further details

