#### **5. TREATMENT PLAN**

##### **5.1 Overall design**

This is an open label, phase II, single arm, and single institution study investigating daily alternating IMiD™ agent therapy with thalidomide and lenalidomide plus rituximab in untreated CLL patients requiring treatment as outlined in the IWCLL update of the 1996 NCI-Working Group criteria for CLL [15]. Half of the patients (odd numbered subjects) will start with a two week course of single agent thalidomide and the other half of the patients (even numbered subjects) will start with a two week course of single agent lenalidomide in order to perform correlative studies to elucidate the

mechanisms of action of thalidomide and lenalidomide. Daily alternating IMiD™ agent therapy will begin with cycle 2 as follows:

- Cycle -1: half of the patients (odd numbered subjects) will receive thalidomide 50 mg PO daily on days 1-14, followed by no treatment days 15-28 and the other half of the patients (even numbered subjects) will receive lenalidomide PO daily on days 1-14, followed by no treatment days 15-28. The lenalidomide dose will be based on baseline calculated creatinine clearance\*.
- Cycles 1 and all escalation cycles: Patients will receive thalidomide 50 mg (every **ODD** day on Days 1-28 of a 28 day cycle: Days 1, 3, 5, 7, 9, 11, 13, 15, 17, 19, 21, 23, 25 & 27) with lenalidomide (every **EVEN** day on Days 1-28 of a 28 day cycle: Days 2, 4, 6, 8, 10, 12, 14, 16, 18, 20, 22, 24, 26 & 28). Each cycle will be 28 days in length. Patients who received lenalidomide during Cycle -1 will receive the same dose of lenalidomide starting with Cycle 1. For patients who did not receive lenalidomide during Cycle -1, lenalidomide will be initiated at a starting dose based on baseline calculated creatinine clearance\*.
- Cycle 1: Patients will also receive rituximab 375 mg/m^2 IV on Days 1, 8, 15 and 22 (+/- 2 days) and then again on the same weekly x 4 schedule every 6th cycle through Cycle 19 (Cycle 7, 13, and 19).

\*\*\*\* Rituximab can be given +/- 2days.

\*\*\*\*All correlative work must be drawn prior to Rituximab administration regardless of the day Rituximab is given.

\*The lenalidomide starting dose will be based on baseline calculated creatinine clearance as follows:

Lenalidomide Starting Dose Based on Renal Function at Study Entry	
Baseline Calculated Creatinine Clearance (by Cockcroft-Gault)	Starting Lenalidomide Dose

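### Section 9 credits Cycle 1 changes to the IMiDs, but rituximab starts in the same cycle, so the Day 15 changes (and nominally the Day 2 changes) are confounded

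*Combined protocol and SAP*

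**What the plan says.** Three items in Section 9 name the IMiDs (thalidomide and lenalidomide) as the cause of what is measured:

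- Item 3 (p38 MAPK activity, mRNA levels, HuR binding) is headed "Impact of IMiD therapy on TNF Family and cox Family mRNA stability".
- Item 4 states "Changes in RNA expression resulting from the IMiD therapy will be assessed using RNA expression arrays". Its days for CLL cells are "CLL cells: day 1, 2, and 15 of cycles -1 and 1 prior to administration of study drug"; T cells and monocytes have the same days.
- Item 5 states "Changes in gene methylation patterns resulting from IMiD therapy will be assessed using methylation oligomicroarrays (MOMA) at", with the days "Day 1 and 15 of cycles -1 and 1 prior to administration of study drug". Footnote 4 of the Section 10 calendar repeats this attribution for both cycles.

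Section 5.1 has no rituximab in Cycle -1. Its Cycle 1 bullet begins "Patients will also receive rituximab 375 mg/m" and lists Days 1, 8, 15 and 22, each ±2 days. Section 9 ends with a rule on the order of draw and infusion: "All correlative work must be drawn prior to Rituximab administration regardless of the day Rituximab is given".

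The Schema and Section 5.1 explain that the two-week single-agent lead-in exists to supply correlative samples on each IMiD alone. Section 13.3 gives no contrast, baseline or method for any correlative study.

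**The concern.** The secondary objective in Section 1.2 asks how thalidomide and lenalidomide act on CLL lymphocytes. Items 3 to 5 put samples from a rituximab-free cycle and a rituximab-containing cycle under one IMiD label. Neither Section 9 nor Section 13 limits the claim to the first of these. An analyst following the text would report a Cycle 1 change from Day 1 to Day 15 as an IMiD effect, although a CD20 antibody was started over the same two weeks. What is at stake is the mechanism conclusion: rituximab effects could be published as IMiD effects.

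**Working it through.** The plan gives no figure on this point, so there is none to reproduce. The check is a count of infusions before each sample, followed by a rough estimate of antibody carry-over.

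**Inputs.** Sampling days: Section 9, items 3 to 5. Rituximab days: Sections 5.1 and 8.3.7. Window of ±2 days and draw order: Sections 5.1 and 9. Oral dosing on odd and even days: Section 5.1; at bedtime: Section 5.4.1. Half-lives: Section 8.3.2.

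**Step 1: infusions before each Cycle 1 sample.**

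| Sample | Nominal | Over all permitted shifts |
|---|---|---|
| Day 1 | 0 | 0 |
| Day 2 (RNA arrays only) | 1 | 0 or 1 |
| Day 15 | 2 | 2 |

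- *Day 2:* with a shift of +1 or +2 the first infusion falls on Day 2 or Day 3, after the draw. With the other three shifts it comes before the draw.
- *Day 15:* the first infusion is given by Day 1 + 2 = 3 and the second by Day 8 + 2 = 10. The third cannot pull the draw earlier than Day 15 - 2 = 13. Two infusions therefore always precede the sample, and by the draw rule the third always follows it.

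**Step 2: what each comparison contains.**

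- *Cycle -1, Day 2 or Day 15 against Day 1:* one IMiD, no rituximab.
- *Cycle 1 Day 1 against Cycle -1 Day 1:* no rituximab; 14 days on the lead-in drug, then 14 days off.
- *Cycle 1 Day 2 against Day 1:* nominally one bedtime thalidomide dose and one infusion. The first Cycle 1 lenalidomide dose has not yet been taken.
- *Cycle 1 Day 15 against Day 1:* seven thalidomide days (1, 3, …, 13), up to seven lenalidomide days (2, 4, …, 14) and two infusions.

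Write the last change as I + R + IR, for the IMiD effect, the rituximab effect and their interaction. Every patient is scheduled for both components, so the data give only the sum. Subtracting the Cycle -1 change does not recover I, because Cycle -1 is a single agent on another schedule.

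**Step 3: carry-over.** Assume single-phase first-order decay. The share of one dose's peak remaining after h hours is 0.5^(h/t½), with h = 24 at Day 2. At Day 15, h = 336 and h = 168 for the two infusions.

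| t½ (h) | Day 2 | Day 15 |
|---|---|---|
| 11.1 (lower end, first infusion) | 0.223 | about 0 |
| 59.8 (first infusion) | 0.757 | 0.020 + 0.143 = 0.163 |
| 104.6 (upper end, first infusion) | 0.853 | 0.108 + 0.329 = 0.436 (unrounded terms) |
| 174 (after fourth infusion) | 0.909 | 0.262 + 0.512 = 0.774 |

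Section 8.3.2 does not say that these patients had CLL, so the figures are illustrative. The same section reports that pre-infusion concentrations rise over successive infusions in most patients. The confounding does not require antibody still to be present, because cells already lysed stay absent. Section 8.3.3 gives a median lymphopenia duration of 14 days (range 1 to 588), which equals the interval from Day 1 to Day 15.

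**Step 4: selection of CLL cells.** Inclusion criterion 1 requires CD20 co-expression. Section 8.3.1 describes rituximab as binding CD20 on malignant B cells and recruiting effector functions that lyse them. CLL cells still present on Day 15 may therefore be a selected surviving population. Section 8.3.3 reports "Rituximab induced B-cell depletion in 70% to 80% of patients with NHL". That supports the direction of the effect but says nothing about its size or timing in CLL.

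**The case against.** The strongest reply is that the design already deals with this. The lead-in cycle was built to give rituximab-free monotherapy samples, and the sentences at issue cover those samples too, where rituximab does not confound the attribution. No passage plans to pool the cycles, and no contrast is planned at all. All of that is correct, and it is why the remedy is small. It does not remove the problem: the label also covers Cycle 1, and nothing in the plan confines the claim to Cycle -1.

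A second reply is that every sample is drawn before rituximab. The rule can only refer to the infusion due at that draw, since Section 9, item 2 itself schedules a sample just before the fourth infusion.

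Some stronger readings are tempting, but the documents do not support them:

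- *All Cycle 1 samples are affected.* The Day 1 sample precedes all rituximab, and the Day 2 sample can do so within the window.
- *A fixed share of the planned contrasts is lost.* No contrasts are specified, so there is no denominator.
- *Metabolomics (item 6) and PI 3-kinase (item 12) have the same fault.* Neither item attributes its changes to the IMiDs.
- *All assayed cells are survivors of depletion.* The selection argument applies to CLL cells only. For T cells and monocytes what remains is shared exposure to rituximab.

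**Conclusion.** The point holds for Section 9, items 3 to 5. Day 15 changes within Cycle 1, and nominally the Day 2 RNA changes, are confounded with rituximab and cannot be attributed to thalidomide or lenalidomide. A reader might go further and call the attribution false. The documents do not show that: an IMiD effect may well be present, but this design cannot identify it in Cycle 1.

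The Day 15 confounding applies to every patient treated as scheduled. The Day 2 confounding applies wherever the first infusion is not delayed. The size of any bias cannot be computed, because the plan gives no assay effect sizes or variability.

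The conclusion assumes that draws follow the stated rule and that rituximab starts in Cycle 1. One sentence in Section 5.1 starts the alternating IMiDs in cycle 2, while the bullets below it and Section 5.2 say Cycle 1. Those passages must be reconciled, but the infusion counts do not depend on them.

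Cycle -1 is free of rituximab but still an uncontrolled before-and-after comparison, with the prophylactic drugs of Section 5.5.1 starting around the same time. Only a secondary mechanistic objective is affected. The response endpoint, sample size and error rates are not.

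**What to change.** In Section 9, items 3 to 5, and in footnote 4 of Section 10:

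1. Define the IMiD-effect analysis as the within-patient Cycle -1 change, Day 1 to Day 15 (and Day 1 to Day 2 for the RNA arrays), reported separately by lead-in drug. This matches the purpose of Cycle -1 given in the Schema and Section 5.1.
2. Report Cycle 1 Day 2 and Day 15 changes as effects of the thalidomide, lenalidomide and rituximab regimen, not of the IMiDs alone. Record the doses and infusions actually received before each sample, since the nominal Day 2 sample precedes the first Cycle 1 lenalidomide dose.
3. For CLL cells on Day 15, state that the sampled cells may be a selected population.

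The cost is wording. No sample, visit, patient or treatment changes, and the edit can be made after collection provided it precedes analysis. The price is precision: with 24 patients split by odd and even number, each lead-in drug has about 24/2 = 12 patients, so the IMiD-specific results will be descriptive. The effect of the alternating IMiD pair without rituximab cannot be estimated from these samples, and the report should say so.
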